7.6.1 Primary Analyses

The primary aims of the study are to assess the local and systemic toxicity of once and twice daily application of 6% CS gel versus a control gel among HIV-infected women. The control gel provides information regarding signs, symptoms and/or morbidity that may be attributed to normal variation and/or the study procedures or use of applicator rather than the investigational product being studied. Primary data analyses will tabulate the number of primary endpoints — listed in Section 7.2.1 — observed during the study, by study cohort and product assignment within cohorts. All participants who enroll in the study will be included in each tabulation. Individual participants will contribute once to the calculation of event rates.

Additional safety analyses will tabulate the number and type of AEs observed overall and by severity and relationship to product, by cohort and product assignment. AEs that lead to discontinuation of product use and/or study participation will be tabulated separately. The temporal relationship of product application and AE onset, and the duration of symptoms, also will be evaluated. Finally, baseline, Day 7, and Day 14 laboratory measures will be summarized and the change in function, defined as the difference between the baseline and Day 14 measurements, will be described.

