2.0 STUDY OBJECTIVES AND DESIGN

2.1 Primary Objective

The primary objectives of this study are:

- To assess the local toxicity of once and twice daily intravaginal application of 6% CS gel on the vulvar and cervicovaginal mucosa of HIV-infected women versus a control gel.
- To assess the systemic toxicity of once and twice daily intravaginal application of 6% cellulose sulfate gel among HIV-infected women.

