7.6 Data Analysis

All descriptive and inferential statistical analyses will be performed using SAS and StatXact statistical software. All randomized participants will be included in all analyses. In the text below, the term "treatment group" refers to a given frequency of a particular product, for sexually abstinent and sexually active participants separately. Secondary analyses will be performed that combine cohorts.

When the use of descriptive statistics to assess group characteristics or differences is required, the following methods are to be used: for categorical variables, the number and percent in each category; for continuous variables, the mean, median, standard deviation, quartiles, and range (minimum, maximum). Within-treatment group assessment of the change from the baseline measurement to the final follow-up measurement will be analyzed using McNemar's test (for categorical response variables) or the paired t-test (for continuous response variables). When the use of formal testing to assess differences between the control gel and CS gel arms is required, the following methods are to be used: for binomial response variables, chi-square tests and logistic regression; for continuous variables, t-tests and linear regression.

Control gel and CS gel participants within each cohort will be compared for baseline characteristics including demographics, pelvic examination, colposcopy, and laboratory measurements using descriptive statistics. Due to the small size of each cohort, formal comparisons will not be performed.

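### The primary aim compares CS gel with a control gel, but no between-gel estimate or interval is planned for any primary endpoint, and the pooled randomised contrast is not assigned to them

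*Protocol*

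**What the plan says.** Protocol Section 2.1 states the local-toxicity objective as a comparison: "6% CS gel on the vulvar and cervicovaginal mucosa of HIV-infected women versus a control gel". The systemic objective there names no comparator ("To assess the systemic toxicity of once and twice daily intravaginal application of 6% cellulose sulfate gel among HIV-infected women"), but Sections 7.2.1 and 7.6.1 restate the local and systemic aims together, both against the control gel.

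Section 7.6.1 gives the primary analysis: "Primary data analyses will tabulate the number of primary endpoints", split "by study cohort and product assignment within cohorts". Each woman counts once towards an event rate. No between-gel difference, ratio, interval or test is named for these endpoints.

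Section 7.6 lists methods for use when formal testing between the gels is required: "for binomial response variables, chi-square tests and logistic regression". It does not say that such testing is required for a primary endpoint. It adds "Secondary analyses will be performed that combine cohorts", without saying of which endpoints. Section 7.6.2 then describes between-gel comparisons for adherence and acceptability (combining cohorts, with covariates for frequency of use and sexual activity) and for HIV RNA and Nugent score. Safety is not among them.

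The Letter of Amendment of 1 August 2003 sets 12, 12, 6 and 10 women per gel in Cohorts 1 to 4.

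**The concern.** Section 7.6.1 says the control gel is there to show what normal variation, study procedures and applicator use produce without the investigational product. Separating those from a product effect is a between-gel contrast, and it is the one quantity that the primary analysis does not name. A reader of the tables can subtract two percentages in each cohort but gets no measure of uncertainty, and each cohort alone is too small to be informative. The randomised contrast over all cohorts, which is the best evidence the trial will have on its primary aim, is described for secondary and exploratory endpoints only.

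A smaller matter follows. If someone does test a rare binary safety endpoint between gels, the methods that Section 7.6 names are poorly suited to counts with zeros.

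**Working it through.** **Inputs.** Women per gel: 12, 12, 6, 10 (Letter of Amendment, 1 August 2003), so 12 + 12 + 6 + 10 = 40 per gel. Illustrative event rates of 1% to 45%, with 5% as the worked example (Section 7.3). The event counts in step 2 and the 5% versus 25% or 35% contrasts in step 3 are assumptions chosen to show scale.

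**1. The plan's own figures.** For n = 12 at 5%: P(0) = 0.95^12 = 0.540, P(≥1) = 0.460, P(≥2) = 0.118. P(0 or 1 event) is 0.882 at 5% and 0.042 at 35%. These match the stated 0.54, 0.46, 0.12 and 88% power. All of them describe one gel group alone. Section 7.3 gives no between-gel precision or power.

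**2. Precision of the CS-minus-control risk difference.** Newcombe's 95% interval combines the Wilson limits (l, u) of the two gels. With the same observed rate p in both, its half-width is √[(p − l)² + (u − p)²].

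| Events per gel | Wilson limits | Half-width |
|---|---|---|
| 1/6 | 3.0% to 56.4% | 42 points |
| 1/10 | 1.8% to 40.4% | 32 points |
| 1/12 | 1.5% to 35.4% | 28 points |
| 2/40 pooled | 1.4% to 16.5% | 12 points |
| 5/40 pooled | 5.5% to 26.1% | 15 points |

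For 1/12: √[(0.0833 − 0.0149)² + (0.3539 − 0.0833)²] = 0.279. The pooled rows ignore stratification and serve as a guide to size.

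**3. Power of a between-gel contrast.** Fisher's exact test, two-sided 0.05, full enumeration.

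| Per gel | 5% v 25% | 5% v 35% |
|---|---|---|
| 6 | under 1% | 2% |
| 10 | 5% | 16% |
| 12 | 9% | 26% |
| 40 pooled | 65% | 92% |

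**4. Zero events.** With the same true rate p in both gels, P(at least one gel has no events) = 1 − [1 − (1 − p)^n]².

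| Per gel | p = 5% | p = 10% | p = 25% |
|---|---|---|---|
| 6 | 93% | 78% | 32% |
| 10 | 84% | 58% | 11% |
| 12 | 79% | 48% | 6% |
| 40 pooled | 24% | 3% | under 1% |

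For n = 12 at 5%: 1 − (1 − 0.540)² = 0.789. In these cases the maximum-likelihood odds ratio has no finite non-zero value. It is zero or infinite if one gel has no events, and undefined if both have none. At 6 per gel and 5%, both gels are empty with probability 0.735² = 54%, which is most of the 93%. In a simulation of the pooled model with covariates for frequency and sexual activity, at least one coefficient was not finite in about 45% of trials at 5%, 9% at 10% and 1% at 15%.

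**The case against.** Four arguments count against this point.

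- **Descriptive reporting is normal in Phase I.** Section 7.3 is built on single-group rates, and the control gel serves as background. This is fair, and it is why the tabulations should stay. It does not supply the contrast that the stated aim asks for.
- **The gels are already shown side by side.** A reader might infer from the word tabulate that the trial can say nothing about relative toxicity. The documents do not support that: rates by gel appear in every cohort and the difference can be read off. What is absent is a planned estimate with its uncertainty, and the pooled version.
- **The logistic model may never be applied to safety.** A reader might infer that the plan's model will fail at its planned event rate. That goes too far. Section 7.6 makes testing conditional and ties none to a primary endpoint. The 5% figure is a worked example within a 1% to 45% grid. Section 1.2 reports colposcopic findings in 1/12 and 2/12 women on CS gel and 3/12 on K-Y Jelly. At those rates the chance of at least one empty gel is about 14% to 37% with 12 per gel and at most about 3% pooled. This trial counts only findings judged related to product, so its rates may be lower.
- **A statistical analysis plan may settle it.** Choosing between exact and asymptotic methods is commonly left there, and StatXact is already named. But Section 7.6.2 shows that the protocol does state between-gel comparisons where it wants them, and it states them for every endpoint group except the primary one.

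**Conclusion.** The point holds as a mismatch between aim and analysis. The primary aim is comparative, the stated primary analysis contains no between-gel estimate or interval, and the pooled contrast is spelled out only for lower-ranked endpoints. The gain from adding it is material: half-widths of about 12 to 15 points against 28 to 42 in single cohorts, and about 92% power for an assumed 5% versus 35% against 2% to 26%. These figures assume full accrual of 40 per gel and the event counts shown. Even pooled, the trial would be informative only about large differences.

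The choice of method for sparse binary data is secondary. It matters if formal testing is done at rates near 5% or below, and it fades quickly at higher rates and with pooling.

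**What to change.** In Section 7.6.1, keep the tabulations by cohort and product. For each primary endpoint add the CS-minus-control risk difference with an exact or score 95% confidence interval, per cohort and pooled over the four cohorts with stratification by cohort.

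In Section 7.6, state that any formal between-gel test of a sparse binary endpoint will use an exact test, and that any regression will be exact or Firth logistic regression, in place of the chi-square test and logistic regression now named.

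The cost is some analysis wording and a few table rows, with no change to sample size or procedures. The drawback is that the pooled estimate averages over frequency of use and sexual activity, so it could hide a difference confined to one regimen. The cohort rows must therefore stay beside it.

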As noted in Section 2.4 up to 96 **80** female participants and up to 48 **32** male partners will be included in this study. Female participants will be enrolled into four cohorts, of 24 women each, Cohorts 1 and 2 consisting of 24 women each, Cohort 3 consisting of 12 women, and Cohort 4 consisting of 20 women. Within each cohort Cohorts 1 and 2, accrual of six participants at each of the four study sites is targeted, within Cohort 3, accrual of three participants at each of the four sites is targeted, and with Cohort 4, accrual of 5 participants at each of the four study sites is targeted. If for some reason a site experiences difficulty reaching its accrual targets, consideration will be given to shifting enrollment "slots" to the other sites, with prior approval of the Protocol Chair.

Ideally, at At each site, three of the six participants enrolled in each cohort, Cohorts 1 and 2, at most two of the three participants enrolled in Cohort 3, and at most three of the five participants enrolled in Cohort 4 will be assigned at random to apply CS gel at the assigned frequency (once or twice daily). The other three women in each cohort will be assigned to apply the control gel. Also at each site, accrual of each cohort will proceed sequentially, after the completion of follow-up of all participants in the prior cohorts, provided accrual is not suspended per the provisions of Section 2.4.3.

As a means to characterize the statistical properties of this study Cohorts 1 and 2, the following table presents the probability of observing zero, at least one, and two or more safety endpoints among groups of 12 women for various "true" event rates:

Event Rate	P (0 events n=12)	P (≥1 event n=12)	P (> 2 events n=12)
1%	0.89	0.11	0.01
5%	0.54	0.46	0.12
10%	0.28	0.72	0.34
15%	0.14	0.86	0.56
25%	0.03	0.97	0.84
35%	0.01	0.99	0.96
45%	< 0.01	>0.99	0.99

For example, if the true rate of a given endpoint in **Cohorts 1 or 2** is five percent, the probability that the endpoint will be observed in at least one of 12 women is 0.46. In addition, with a true rate of five percent, 12 women provide 88 percent power to exclude endpoint rates greater than 35 percent (i.e., the probability of observing 0 or 1 endpoint is less than 0.05 when the true rate is 35 percent, while this probability is 0.88 when the true rate is five percent).

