Participants who complete twice daily administration of the assigned product on each study day between the Enrollment Visit (inclusive) and the Day 14 Followup Visit, as well as participants who adhere to one of the scenarios described above, will be considered adherent to the product use regimen. Participants who experience an AE that requires temporary suspension of product use at the instruction of the investigator for more than two days, but who are able to complete a total of 14 days of product use at the assigned frequency following resolution of the AE, prior to onset of the next menstrual period, also will be considered adherent. As well, participants who experience an AE that requires permanent product discontinuation, but completed daily administration at the assigned frequency on the days preceding the AE will be considered adherent.

For the sexually active cohorts (required to have vaginal intercourse at their usual weekly rate that must be at least twice per week), adherence is further defined as having at least two episodes of vaginal intercourse during the 14-day exposure period.

Non-adherent participants will be asked their reasons for non-adherence and this information will be recorded on study case report forms. If the participant is not willing to become adherent, the participant will be withdrawn from the study as described in Section 3.7. Non-adherent participants will not be replaced.

Note: Participants in the sexually active cohorts who have fewer than two episodes of vaginal intercourse between study Days 0 and 6 will be encouraged to resume their usual frequency of intercourse between Days 7 and 13.

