7.3 Accrual, Follow-up, and Sample Size

As noted in Section 2.4 up to 96 female participants and up to 48 male partners will be included in this study. Female participants will be enrolled into four cohorts of 24 women each. Within each cohort, accrual of six participants at each of the four study sites is targeted. If for some reason a site experiences difficulty reaching its accrual targets, consideration will be given to shifting enrollment "slots" to the other sites, with prior approval of the Protocol Chair.

At each site, three of the six participants enrolled in each cohort will be assigned at random to apply CS gel at the assigned frequency (once or twice daily). The other three women will be assigned to apply the control gel. Also at each site, accrual of each cohort will proceed sequentially, after the completion of follow-up of all participants in the prior cohorts, provided accrual is not suspended per the provisions of Section 2.4.3.

As a means to characterize the statistical properties of this study, the following table presents the probability of observing zero, at least one, and two or more safety endpoints among groups of 12 women for various "true" event rates:

Event Rate	P (0 events n=12)	P (≥1 event n=12)	P (≥2 events n=12)
1%	0.89	0.11	0.01
5%	0.54	0.46	0.12
10%	0.28	0.72	0.34
15%	0.14	0.86	0.56
25%	0.03	0.97	0.84
35%	0.01	0.99	0.96
45%	< 0.01	>0.99	0.99

For example, if the true rate of a given endpoint is five percent, the probability that the endpoint will be observed in at least one of 12 women is 0.46. In addition, with a true rate of five percent, 12 women provide 88 percent power to exclude endpoint rates greater than 35 percent (i.e., the probability of observing 0 or 1 endpoint is less than 0.05 when the true rate is 35 percent, while this probability is 0.88 when the true rate is five percent).

The statistical properties of this study also may be characterized by the width of confidence intervals (CI) around observed event rates. The following table presents the exact 95 percent CIs around endpoint rates when zero, one, or two endpoints are observed among 12 women:

No. Endpoints Observed	Lower Bound of CI	Upper Bound of CI
0	0.0%	26.5%
1	0.2%	38.5%
2	2.1%	48.4%

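### Section 7.6.1 counts every enrolled woman in each toxicity tabulation with no condition on having been examined, which biases the pelvic/colposcopic and laboratory rates downward if any woman is never assessed

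*Protocol*

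**What the plan says.** Protocol Section 7.6 sets the general analysis population: "All randomized participants will be included in all analyses". Section 7.6.1 repeats this for the toxicity endpoints: "All participants who enroll in the study will be included in each tabulation". The numerator is a count of what was seen ("Primary data analyses will tabulate the number of primary endpoints"), by cohort and product, and the unit is the woman: "Individual participants will contribute once to the calculation of event rates". Neither section says how a woman with no follow-up exam or blood result is to be shown.

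Section 7.2.1 lists four primary endpoints. Two of them, pelvic/colposcopic findings and Grade 3 or higher laboratory values, can be observed only in a woman assessed after Enrollment. The first scheduled assessment is the Day 7 visit, allowed from Day 5 to Day 9 (Section 5.4).

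Loss before that visit is possible. Section 3.7 lets a woman withdraw at any time, or be withdrawn by the investigator. It asks sites to try for a final evaluation but cannot guarantee one. Section 4.4 adds: "If the participant is not willing to become adherent, the participant will be withdrawn from the study as described in Section 3.7". Non-adherent women are not replaced.

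The groups are small. The letter of amendment of 1 August 2003 gives "Cohorts 1 and 2 consisting of 24 women each, Cohort 3 consisting of 12 women, and Cohort 4 consisting of 20 women", that is 12, 12, 6 and 10 women per product.

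**The concern.** In a toxicity study, a denominator that includes women in whom the endpoint could not have been seen errs towards reassurance. With 6 to 12 women per product, one or two unseen women visibly shift the rate and its exact upper limit.

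The sample-size argument is also affected. Section 7.3 states that "12 women provide 88 percent power to exclude endpoint rates greater than 35 percent" when the true rate is 5%, and rests this on the claim that "the probability of observing 0 or 1 endpoint is less than 0.05 when the true rate is 35 percent". That claim supposes all 12 women were observed. Section 7.3 does consider a smaller effective number when two women are non-adherent, but makes no allowance for women who were never assessed.

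**Working it through.** **Inputs.** Group sizes of 12, 6 and 10 per product, the exclusion rule (0 or 1 endpoint), the excluded rate (35%), the assumed true rate (5%) and the 0.05 limit all come from Section 7.3 and the 1 August 2003 letter. The documents give no dropout rate. The number unseen, m, is therefore an assumption, taken as 0 to 3 of 12. Unseen women are first assumed to have the same risk as the others.

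**Step 1: reproduce the plan's figures.** With k women observed and true rate p,

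P(0 or 1) = (1−p)^k + k·p·(1−p)^(k−1).

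- k = 12, p = 0.05: 0.882, the stated 88%.
- k = 12, p = 0.35: 0.65^12 + 12 × 0.35 × 0.65^11 = 0.042, below 0.05 as stated.
- Exact (Clopper–Pearson) 95% upper limits for 0, 1 and 2 events in 12: 26.5%, 38.5%, 48.4%, as printed.

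**Step 2: apply the same rule when m of the 12 are unseen but stay in the denominator.** Only k = 12 − m women can show an event. The expected tabulated rate is p × (12 − m)/12.

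| m unseen of 12 | P(0 or 1) at true 35% | Expected tabulated rate at true 25% |
|---|---|---|
| 0 | 0.042 | 25.0% |
| 1 | 0.061 | 22.9% |
| 2 | 0.086 | 20.8% |
| 3 | 0.121 | 18.8% |

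The 0.05 limit is passed with the first unseen woman. The probability of 0 or 1 event at a true 5% rate also rises, from 0.882 to 0.898, 0.914 and 0.929. Losing observations therefore makes the product look easier to clear.

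**Step 3: rate and exact 95% upper limit, by denominator.**

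| Group | Unseen | Events | All enrolled | Assessed only |
|---|---|---|---|---|
| n = 12 | 1 | 1 | 8.3% (38.5%) | 9.1% (41.3%) |
| n = 12 | 2 | 0 | 0% (26.5%) | 0% (30.8%) |
| n = 12 | 2 | 1 | 8.3% (38.5%) | 10.0% (44.5%) |
| n = 12 | 2 | 2 | 16.7% (48.4%) | 20.0% (55.6%) |
| n = 12 | 3 | 1 | 8.3% (38.5%) | 11.1% (48.2%) |
| n = 6 (Cohort 3) | 1 | 1 | 16.7% (64.1%) | 20.0% (71.6%) |
| n = 10 (Cohort 4) | 2 | 1 | 10.0% (44.5%) | 12.5% (52.7%) |

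The amendment's Cohort 4 table gives the same limits for groups of 10, except for last-digit rounding at 0 of 10 (30.9% printed).

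**Step 4: drop the equal-risk assumption.** With 1 observed event and 2 unseen of 12, the rate is 1/12 = 8.3% if both unseen women are scored event-free, 1/10 = 10.0% among those assessed, and 3/12 = 25.0% if both had events. The assessed-only figure is not an upper bound.

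**The case against.** The case against has five parts.

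- **The scoring is inferred.** No sentence says unassessed women are event-free. A table could include a woman as not assessed, and an analysis plan not seen here may say so. This is fair as far as it goes. The protocol does, however, fix the population for every tabulation, and an assessed-only rate would sit awkwardly with that wording.
- **Few women are exposed to the problem.** A reader might infer that every withdrawn woman counts as event-free. The documents do not support that. An event seen before withdrawal is counted. Adherence is reviewed at the Day 7 and Day 14 visits (Section 4.4), which themselves include the colposcopy and bloods (Sections 5.4 and 5.5), so withdrawal for non-adherence does not imply a missing exam. The gap is mainly women who leave before the Day 5–9 visit and have no final evaluation.
- **Irritation would usually be caught.** Related symptoms and related adverse experiences are primary endpoints in their own right. Genital complaints trigger an interim pelvic exam (Section 5.7), women who stop product stay in follow-up (Section 4.5), and events leading to discontinuation are tabulated separately (Section 7.6.1). This stands, although Section 6.2 ends active safety follow-up one day after the last application, which weakens the Section 4.5 safeguard somewhat.
- **No conclusion rests on the confidence limits.** A reader might infer that the exact limits decide safety. Section 7.6.1 specifies counts only. The limits in Section 7.3 illustrate the design, and the accrual-suspension rule in Section 6.1 counts women without a denominator.
- **All-enrolled counting is a usual safety convention, and the alternative is biased too.** Both are true. If toxicity drives withdrawal, the assessed-only rate is also too low. This argues for adding to the all-enrolled count, not replacing it.

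**Conclusion.** The point holds for two of the four primary endpoints, the pelvic/colposcopic and laboratory ones, and only for women with no post-Enrollment assessment of that type and no earlier observed event. For them the stated rule biases the rate downward.

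The size depends on an assumed number unseen. Under equal risk, one unseen woman of 12 takes the error probability of the Section 7.3 rule from 0.042 to 0.061, above its stated limit. Two unseen women lower the upper limit for one event from 44.5% to 38.5%. If the 100% retention target in Section 3.6 is met, nothing changes.

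Two further readings are not supported. The two-women scenario in Section 7.3 concerns non-adherence and is not an expected number of missing exams. Heavier loss in the more irritating arm is plausible, but nothing in the protocol shows it.

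**What to change.** In Section 7.6.1, keep the all-enrolled count. For the pelvic/colposcopic and laboratory endpoints, also report by cohort and product:

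1. the number of women with at least one post-Enrollment assessment of that type;
2. the event rate among those women, with its exact confidence interval;
3. one worst-case table in which unassessed women are counted as events, because the assessed-only rate is itself too low if toxicity drives withdrawal.

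This takes about two sentences and one extra table. Visits and treatment do not change. If any woman is unassessed, the reported upper limits will be somewhat less favourable.

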7.6.2 Secondary Analyses

Participant adherence to the product use regimen will be assessed within treatment group and comparisons will be made between the control gel and CS gel groups combining the cohorts with covariates for frequency of use and sexual activity. Similar analyses will be performed on the endpoints assessing acceptability. These include male and female participants' willingness to use the assigned product during intercourse in the future (as reported via questionnaire on study Day 14), reported positive aspects of using the assigned product, and reported negative aspects of using the assigned product (as reported via questionnaire). In addition, participants' preferences at Enrollment will be compared with acceptability after having used the study gels.

To explore potential effects of product use on cervicovaginal shedding of HIV, change in the number of copies of HIV RNA from baseline to Day 7 and Day 14 will be analyzed within each treatment group. In addition, the change in the number of copies of HIV RNA will be compared between the control gel and CS gel users and for sexually active and sexually abstinent women.

Similarly, to explore potential effects of product use on vaginal flora, change in Nugent scores from baseline to Day 7 and Day 14 will be analyzed within each treatment group. In addition, change in score will be compared between the control gel and CS gel users and for sexually active and sexually abstinent women.

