8.2 Informed Consent

Written informed consent will be obtained from each study participant prior to the initiation of any study procedures. Each study site is responsible for developing study informed consent forms for local use, based on the samples in Appendix II, which describes the purpose of the study, the procedures to be followed, and the risks and benefits of participation, in accordance with all applicable regulations. Participants will be provided with a copy of their informed consent form if they are willing to receive it. Study staff will document the informed consent process as described in the Study-Specific Procedures Manual.

Female participants may experience discomfort when having pelvic exams and/or undergoing phlebotomy for this study. During phlebotomy, they also may feel dizzy or faint, or develop a bruise or swelling where the needle is inserted; there is a very small chance of the participant getting an infection at the site where the blood is drawn.

Male and female participants may become embarrassed, worried, or anxious when receiving HIV and STD counseling. They also may become worried or anxious while waiting for their HIV and STD test results. Study staff will assist participants in dealing with these feelings.

Based on the prior completed Phase I vaginal study of CS gel versus K-Y Jelly, potential risks to female participants associated with use of the study products include vulvar and/or vaginal redness, itching, burning, or pain; abnormal vaginal bleeding; and abdominal pain and tenderness. For male participants, although exposure to the study products should occur rarely, if at all, given instructions to use male condoms during each act of vaginal intercourse while in the study, the prior Phase I penile study of CS gel indicated that mild penile tingling or stinging may occur if men are exposed to CS gel.

CS gel has been shown to have anticoagulant effects *in vitro*. Although no such effects were observed in the prior Phase I study among HIV-uninfected women, it is possible, that such effect could be observed among participants in this study.

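### Section 7.6.1 requires no CS-minus-control estimate of change in laboratory measures; the change is only described, and the one test tied to change from baseline is within group

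*Protocol*

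**What the plan says.** - **Section 7.6.1** summarises the laboratory measures at baseline, Day 7 and Day 14 and adds that "the change in function, defined as the difference between the baseline and Day 14 measurements, will be described". The sentence names no contrast between gels. The same section states the primary aims, local and systemic toxicity, as relative to a control gel. It gives the control gel the task of showing what normal variation, study procedures and the applicator would produce.
- **Section 7.6** on change from baseline: "Within-treatment group assessment of the change from the baseline measurement to the final follow-up measurement will be analyzed using" McNemar's test for categorical variables or the paired t-test for continuous ones. It explains that "the term 'treatment group' refers to a given frequency of a particular product", separately for abstinent and sexually active women. That makes eight groups, four per gel.
- **Section 7.6** on comparisons between gels: it lists t-tests and linear regression for continuous variables, conditionally: "When the use of formal testing to assess differences between the control gel and CS gel arms is required". No section requires this for laboratory change.
- **Section 7.6.2** does require it for two exploratory endpoints: "the change in the number of copies of HIV RNA will be compared between the control gel and CS gel users", with a parallel sentence for the Nugent score.
- **Section 7.2.1** makes related grade 3 or higher laboratory values, coagulation included, a primary endpoint, which Section 7.6.1 tabulates by cohort and product.
- **The risk text after Section 8.2** notes the anticoagulant action of CS in vitro and says "it is possible, that such effect could be observed among participants in this study".

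**The concern.** The women are randomised individually to CS or control gel and bled on the same schedule, so the trial can separate a gel effect from whatever else changes over two weeks. A before/after difference within one gel cannot do this: it contains the gel effect plus anything common to both gels.

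Some common change is plausible. Enrollment is set 2 to 6 days after menses and the last visit falls around Day 14, so the two samples come from different points in the cycle, with further blood drawn in between.

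Two misreadings are then possible. A significant change in APTT, PT or haemoglobin among CS women could be a shared shift. A flat result could hide a gel effect offset by one. The by-product counts do not close the gap for coagulation, because a related grade 3 or higher value is a threshold event and a smaller movement in PT or APTT need not reach it.

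**Working it through.** **The plan's own figure.** The protocol gives no power or precision statement for laboratory change. The nearest stated figure is 88% power for 12 women to exclude an event rate above 35% when the true rate is 5% (Section 7.3). It reproduces: P(X ≤ 1 | n=12, 5%) = 0.882 and P(X ≤ 1 | n=12, 35%) = 0.042. It concerns single-group event counts and says nothing about mean change.

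**Inputs from the protocol.** CS group sizes as amended on 01 August 2003 are 12, 12, 6 and 10, with the same numbers on control, so 40 v 40 in total.

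**Assumed inputs.** Two-sided 5% level, and a shift s common to both gels of 0.2, 0.3 or 0.5 SD of the change score. The documents give no SD and no expected change.

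**Step 1: paired t-test in one CS group, true gel effect zero.** The statistic is noncentral t with n − 1 degrees of freedom and noncentrality s√n. For n=12 and s=0.5 the noncentrality is 0.5 × √12 = 1.732 and the critical value is 2.201, giving a rejection probability of 0.353.

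| n in CS group | s = 0.2 | s = 0.3 | s = 0.5 |
|---|---|---|---|
| 12 (Cohorts 1, 2) | 0.097 | 0.158 | 0.353 |
| 10 (Cohort 4) | 0.088 | 0.136 | 0.293 |
| 6 (Cohort 3) | 0.069 | 0.093 | 0.171 |

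**Step 2: between-gel contrast under the same shift.** Expected change is s in both gels, so the expected difference is s − s = 0 and the test rejects in 5% of cases whatever s is.

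**Step 3: precision of that contrast.** The 95% CI half-width for a difference in mean change, in SD of change, is t(0.975, 2n − 2) × √(2/n).

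- One cohort, 12 v 12: 2.074 × √(2/12) = 0.85 SD.
- Four cohorts pooled, 40 v 40: 1.991 × √(2/40) = 0.45 SD.

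**Step 4: gain from baseline adjustment.** At 40 v 40 the difference detectable with 80% power is 0.634 SD of the laboratory value without adjustment. Adjusting for baseline multiplies it by √(1 − r²), where r is the assumed correlation between baseline and follow-up: 0.634 × √0.75 = 0.55 SD at r = 0.5, and 0.634 × √0.51 = 0.45 SD at r = 0.7.

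**The case against.** Several points on the other side are sound.

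- A reader might infer that a shift shared by both gels would be credited to CS gel. No text says so. A treatment group can be either product, so the control groups get the same summary, and a careful reader would look at both.
- A reader might infer that a gel effect cannot be separated from a shared shift. It can: the data are randomised and concurrent, and Section 7.6 already lists between-gel t-tests and linear regression and foresees secondary analyses that combine cohorts. What is missing is a sentence applying them to laboratory change.
- It is not certain that a paired t-test is planned for these measures. Section 7.6.1 says described, whereas Section 7.6.2 says analysed for HIV RNA and Nugent score. The rates in Step 1 therefore hold only if the general rule in Section 7.6 is applied to laboratory change.
- A within-CS test on all 40 women would inflate more, but no section plans one, so no figure for it is used here.
- By-product safety data are not confined to grade 3 values. All AEs are tabulated by cohort and product, and the AE definition in Section 6.2 can include an abnormal laboratory finding.
- The systemic-toxicity objective in Section 2.1 does not mention the control gel. Sections 7.2.1 and 7.6.1 do.
- Description is a defensible choice in a Phase I study, and a SAP that is not shown may name the contrast.

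The sentence "Due to the small size of each cohort, formal comparisons will not be performed" is no defence: it stands in the paragraph on baseline characteristics.

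These points limit the finding but do not remove it. Section 7.6.1 does say how laboratory change is handled, and a SAP that followed it would not have to produce the comparison on which that section's own aim depends. Setting a significant paired test in one gel beside a non-significant one in the other is no substitute for an estimate of the difference.

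**Conclusion.** The point holds as a gap in the analysis text. The protocol requires no CS-minus-control estimate of laboratory change, while it requires one for two exploratory endpoints and frames the systemic-toxicity aim against control in Sections 7.2.1 and 7.6.1. It matters most for PT and APTT, where the protocol itself raises a possible effect and a shift below grade 3 need not appear in the counts.

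The size is conditional on two things: that the paired test is applied to laboratory measures, and that a common shift of 0.2 to 0.5 SD of change exists. Both the shift and its range are assumptions. At the low end the inflation is modest, 7% to 10% across group sizes; at 0.5 SD it reaches 17% to 35%. The improvement is worth making, but the design does not depend on it.

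**What to change.** In Section 7.6.1, replace the statement that the change will be described with text to this effect:

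- For each laboratory measure, PT and APTT first, estimate the CS-minus-control difference at Day 14, and also at Day 7, by linear regression on gel, the Enrollment value of that measure and cohort. Pool the four cohorts and report each estimate with a 95% CI.
- Show the change by gel within each cohort beside it.
- State that within-gel changes, and any paired t-tests on them, are descriptive and will not be read as evidence for or against a gel effect.
- Label the intervals as estimation without multiplicity control.
- Note that the pooled estimate averages once-daily and twice-daily use. Cohort-level contrasts are too imprecise to carry the conclusion (half-width about 0.85 SD of change at 12 v 12).

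The cost is a few sentences and one regression table, using a method Section 7.6 already lists and blood results already scheduled at Enrollment, Day 7 and Day 14. No visits, samples or participants are added. The drawback is the number of intervals: PT, APTT, five liver and two renal tests at two visits make 9 × 2 = 18 before the blood count, hence the label.
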